#### **4.3 Annual IRB Renewals, Continuing Review and Final Reports**

A continuing review of the protocol will be completed by the University of Chicago IRB and the affiliates' IRBs at least once a year for the duration of the study. The annual IRB renewals for the affiliate institution should be faxed promptly to the Regulatory Affairs Administrator. If the institution's IRB requires a new version of the consent form with the annual renewal the consent form should be included with the renewal letter.

Continuing review reports will include the following: the number of subjects accrued; a description of any adverse events or unanticipated problems involving risks to subjects or others and of any withdrawal of subjects from the research or complaints about the research; a summary of research literature, findings obtained thus far, amendments or modifications since the last review, reports of multi-center trials and any other relevant information, especially information about the risks associated with the research; and a copy of the current informed consent document.

#### **4.4 Departure from the Protocol**

An investigator cannot modify the protocol without satisfying procedures in 4.2. Any changes in research activity, except those necessary to remove an apparent, immediate hazard to the study subject, must be reviewed and approved by the local IRB. When a variation from the protocol is deemed necessary for an individual subject, the principal investigator must be contacted by phone or email ([name], [name], [[contact]](mailto:[contact])). Such contact must be made as soon as possible to permit a decision as to whether or not the subject is to continue in the study.

The principal investigator must be informed of all intentional or unintentional departures from the protocol and will decide whether or not the subject is to continue in the study ([name], [name], [[contact]](mailto:[contact])). All departures from the protocol, intentional and unintentional, along with the decision of the principal investigator will be submitted in a written report to the local and University of Chicago IRB.

#### 4.5 Registration

All patients must be registered with the University of Chicago Study Coordinator at least 48 hours prior to the commencement of treatment. Confirm all selection criteria listed in Section 3.2.2, and then call the Study Coordinator at [contact] with the following information:

Provider of information  
Study # and Institution  
Treating Physician  
Patient name and hospital ID number  
Patient's zip code of residence  
Date of signed informed consent  
Race, gender, date of birth of patient  
Diagnosis and date of initial diagnosis

The Study Coordinator will issue a confirmation of registration. The Study Coordinator will ensure that all necessary supporting documents have been received and that the potential patient is eligible to start treatment on schedule. Photocopies of the appropriate pages of the protocol will be used to determine eligibility. If there are questions about eligibility, the Study Coordinator will question the principal investigator, who will be responsible for any final decisions on eligibility. The date the patient is registered will be considered the patient's "On-Study Date." Patients that sign consent and do not go "On-Study" will be recorded in the database with the date that they signed consent and the reason for not going "On-Study" (either Ineligible or Withdrawn Consent). The treatment start date will also be tracked.

At the time of registration, the registering institution will:

- Confirm that their institution has IRB approval of the correct version of protocol/consent and has an annual update on file.
- Fax or email all required forms (see data submission Section 5) and source documentation for the protocol required eligibility criteria and pre-study procedures, including labs, radiology, pathology reports, and signed consent form to the Study Coordinator's attention.
- Communicate with the Study Coordinator to ensure that all necessary supporting documents have been received and that the potential patient is eligible to start treatment on schedule.

#### 4.6 Reporting of Adverse Events

Serious Adverse Events that require phone reporting within 24 hrs per section 3.4.4.2 should be phoned and emailed to the University Of Chicago Cancer Clinical Trials Office (CCTO) at [contact] and faxed to Novartis Clinical Safety and Epidemiology Department. [contact]) by the end of the business day during which the investigator becomes aware of the event or by 12 noon the following day if the event occurs after normal business hours.

The following information is required when calling in the event:

- Reporter's Name and Telephone Number

- Patient Initials
- Patient Medical Record Number
- IRB Protocol Number
- PI of Study
- Attending Physician
- Date of Event
- Description of Event (including grade of the event and if the event required hospitalization)

Upon receipt of the 24-hour notification, the CCTO will send an e-mail to the research nurse, attending physician, all PI's, and to Novartis Pharmaceuticals CS&E Department [contact]).

All serious adverse events, except those exempted from reporting per section 3.4.4.2, must be reported to the University of Chicago Cancer Center Clinical Trials Office in writing within **10 calendar days of event occurrence (5 calendar days for an unexpected grade 4 or 5 event, or death within 30 days of discontinuing investigational therapy)**. MedWatch form (FDA form 3500A) should be utilized. Report should also be submitted to the affiliate institution's local IRB according to institutional guidelines. Reports should be sent to the address or fax number below with any appropriate source documentation.

Quality Assurance Coordinator  
Cancer Clinical Trials Office  
University of Chicago, MC 1140  
[name]  
[name]  
[contact]  
Email: [[contact]](mailto:[contact])

Adverse Events will be recorded and followed until the adverse event has subsided and abnormal findings have returned to normal or stabilized. In addition, any events with a suspected causal relationship to Novartis study drug will be reported as AEs or SAEs (as applicable) throughout follow-up.

The sponsor will stop the study at any time if new knowledge is obtained indicating that:

- Safety for all participating patients can no longer be assumed; and/or
- The risk-benefit ratio is no longer acceptable for the participating patients.

New adverse events for patients who discontinue the study will not be recorded past their date of discontinuation but events that are ongoing will be followed, if feasible, until they resolve. All patients will be followed for survival.

A weekly report of delinquent or pending documents will be forwarded to [name] (U of C Events Only). All delinquent reporting (greater than 10 days from event occurrence) must include documentation of reason for delinquency and may require implementation of an action plan.

SAEs that have not resolved at the time of reporting should have a follow up written report within 10 calendar days of resolution. This includes any pregnancies in which the outcome, including spontaneous or voluntary termination, details of birth, and the presence or absence of any birth defects, congenital abnormalities or maternal and newborn complications should be reported.

Once the appropriate SAE documents have been received, the University of Chicago Cancer Center Clinical Trials office forwards these to the Principal Investigator. The Principal Investigator should comment on the outcomes of the event or problem including likely relationship to study drug. The Principal Investigator should also indicate whether he/she concurs with the details of the report provided by the study investigator and provide any recommendations for actions to be taken in response to the SAE.

Once the University of Chicago Cancer Center Clinical Trials Office receives the Principal Investigator's report, they will forward all documents to the IRB, research nurse, all participating institutional PI's, the FDA, and Novartis [contact]).

#### **4.6.1 Novartis instructions for rapid notification of serious adverse events**

The principal investigator has the obligation to report all serious adverse events to the FDA, IRB, and Novartis Pharmaceuticals Drug Safety and Epidemiology Department (DS&E).

All events reported to the FDA by the investigator are to be filed utilizing the Form FDA 3500A (MedWatch Form).

**All events must be reported, by [contact]), to Novartis Pharmaceuticals DS&E Department within 24 hours of learning of its occurrence.** This includes serious, related, labeled (expected) and serious, related, unlabeled (unexpected) adverse experiences. All deaths during treatment or within 30 days following completion of active protocol therapy must be reported within 5 working days.

Any serious adverse event occurring after the patient has provided informed consent and until 4 weeks after the patient has stopped study participation must be reported. This includes the period in which the study protocol interferes with the standard medical treatment given to a patient (e.g. treatment withdrawal during washout period, change in treatment to a fixed dose of concomitant medication).

Serious adverse events occurring more than 4 weeks after study discontinuation need only be reported if a relationship to the Novartis study drug (or therapy) is suspected.

For Comparator Drugs/Secondary Suspects (Concomitant Medications), all serious adverse experiences will be forwarded to the product manufacturer by the investigator.

##### **4.6.1.1 Pregnancies**

Any pregnancy that occurs during study participation should be reported. To ensure patient safety each pregnancy must also be reported to Novartis within 24 hours of learning of its occurrence. The pregnancy should be followed up to determine outcome, including

spontaneous or voluntary termination, details of the birth, and the presence or absence of any birth defects, congenital abnormalities, or maternal and/or newborn complications.

#### 4.6.1.2 Testing for Hepatitis

##### **Hepatitis B Virus testing**

Prior to randomization the categories of patients listed in Section 3.2 should be tested for hepatitis B serologic markers and viral load: HBV-DNA HBsAg, HBc Ab, and HBs Ab.

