- Chronic or active hepatitis B or C. Note: A detailed assessment of Hepatitis B/C medical history and risk factors must be done at screening for all patients. HBV DNA and HCV RNA PCR testing are required at screening for all patients with a positive medical history based on risk factors and/or confirmation of prior HBV/HCV infection (see Section 4.6.1.2).
- A known history of HIV seropositivity
- Impairment of gastrointestinal function or gastrointestinal disease that may significantly alter the absorption of Everolimus (e.g., ulcerative disease, uncontrolled nausea, vomiting, diarrhea, malabsorption syndrome or small bowel resection)
  - N.B.: patients are allowed to administer everolimus through a feeding tube (see Appendix A)
- Patients with an active, bleeding diathesis
- Female patients who are pregnant or breast feeding, or adults of reproductive potential who are not using effective birth control methods. Adequate contraception must be used throughout the trial by both sexes and for at least 8 weeks after the last dose of study drug, by both sexes. Hormonal contraceptives are not acceptable as a sole method of contraception. (Women of childbearing potential must have a negative urine or serum pregnancy test within 7 days prior to administration of Everolimus)
- Male patient whose sexual partner(s) are WOCBP who are not willing to use adequate contraception, during the study and for 8 weeks after the end of treatment
- Patients who have received prior treatment with an mTOR inhibitor (sirolimus, temsirolimus, everolimus).
- Patients with a known hypersensitivity to Everolimus or other rapamycin analogues (sirolimus, temsirolimus) or to its excipients
- History of noncompliance to medical regimens
- Patients unwilling to or unable to comply with the protocol

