### **3.2.5 Known Undesirable Side Effects of Everolimus**

The data described below reflect exposure to everolimus (n=274) and placebo (n=137) in a randomized phase III study for the treatment of metastatic renal cell carcinoma. In total, 165 patients were exposed to everolimus 10 mg/day for  $\geq$ 4 months. The median age of patients was 61 years (range 27 to 85). The most common adverse reactions (incidence  $\geq$ 10%) were stomatitis, rash, fatigue, asthenia, diarrhea, anorexia, nausea, mucosal inflammation, vomiting, cough, peripheral edema, infections, dry skin, epistaxis, pruritus, and dyspnoea. The most common grade 3-4 adverse reactions (incidence  $\geq$ 2%) were infections, stomatitis, fatigue, and pneumonitis.

The median duration of blinded study treatment was 141 days (range 19 to 451) for patients receiving everolimus and 60 days (range 21 to 295) for those receiving placebo. The rates of treatment-emergent adverse reactions resulting in permanent discontinuation were 7% and 0% for the everolimus and placebo treatment groups, respectively. Most treatment-emergent adverse reactions were grade 1 or 2 in severity. Grade 3 or 4 treatment-emergent adverse reactions were reported in 39% versus 7% of patients receiving everolimus and placebo, respectively. Deaths due to acute respiratory failure (0.7%), infection (0.7%), and acute renal failure (0.4%) were observed on the everolimus arm.

Everolimus has immunosuppressive properties and may predispose patients to bacterial, fungal, viral or protozoan infections, including infections with opportunistic pathogens. Localized and systemic infections, including pneumonia, other bacterial infections, invasive fungal infections, such as aspergillosis or candidiasis and viral infections including reactivation of hepatitis B virus, have been described in patients taking everolimus. Some of these infections have been severe (e.g. leading to respiratory or hepatic failure) and occasionally have had a fatal outcome.

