Physicians and patients should be aware of the increased risk of infection with everolimus. Treat pre-existing infections prior to starting treatment with everolimus. While taking everolimus, be vigilant for symptoms and signs of infection; if a diagnosis of infection is made, institute appropriate treatment promptly and consider interruption or discontinuation of everolimus. If a diagnosis of invasive systemic fungal infection is made, discontinue everolimus and treat with appropriate antifungal therapy.

Reactivation of Hepatitis B (HBV) has been observed in patients with cancer receiving chemotherapy (Yeo 2004). Sporadic cases of Hepatitis B reactivation have also been seen in this setting with everolimus. Use of antivirals during anti-cancer therapy has been shown to reduce the risk of Hepatitis B virus reactivation and associated morbidity and mortality (Loomba 2008). A detailed assessment of Hepatitis B/C medical history and risk factors must

be done for all patients at screening, with testing performed prior to the first dose of everolimus.

Hypersensitivity reactions manifested by symptoms including, but not limited to, anaphylaxis, dyspnea, flushing, chest pain or angioedema (e.g. swelling of the airways or tongue, with or without respiratory impairment) have been observed with everolimus.

Hyperglycemia has been reported in clinical trials. Monitoring of fasting serum glucose is recommended prior to the start of everolimus therapy and periodically thereafter. Optimal glycemic control should be achieved before starting a patient on everolimus. Mouth ulcers, stomatitis and oral mucositis have been seen in patients treated with everolimus. In such cases topical treatments are recommended, but alcohol- or peroxide-containing

Elevations of serum creatinine, usually mild, have been reported in clinical trials. Monitoring of renal function, including measurement of blood urea nitrogen (BUN) or serum creatinine, is recommended prior to the start of everolimus therapy and periodically thereafter.

Decreased hemoglobin, lymphocytes, platelets and neutrophils have been reported in clinical trials. Monitoring of complete blood count is recommended prior to the start of everolimus therapy and periodically thereafter.

Everolimus is not recommended in patients with severe hepatic impairment, (Child-Pugh class C).

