### 3.4 Visit schedule and assessments

#### 3.4.1 Pre-study Procedures

- All patients must have completed curative intent therapy for locally advanced SCCHN 8-16 weeks prior to randomization (as defined in 3.3.5 AND be NED as defined in 3.2.2).
- Tissue must have been collected **PRIOR** to starting curative intent therapy on all patients (see Section 3.4.7)
- A detailed assessment of hepatitis B/C medical history and risk factors must be done for all patients at screening.

Testing for hepatitis B viral load and serologic markers: HBV-DNA, HBsAg, HBs Ab, and HBc Ab and HCV RNA PCR are required at screening for all patients in the following risk categories:

- All patients who currently live in (or have lived in) Asia, Africa, Central and South America, Eastern Europe, Spain, Portugal, and Greece.  
[<http://wwwnc.cdc.gov/travel/yellowbook/2010/chapter-2/hepatitis-b.aspx#849> ]
- Patients with any of the following risk factors:
  - known or suspected past hepatitis B infection,
  - blood transfusion(s) prior to 1990,
  - current or prior IV drug users,
  - current or prior dialysis,
  - household contact with hepatitis B infected patient(s),
  - current or prior high-risk sexual activity,
  - body piercing or tattoos,
  - mother known to have hepatitis B
  - history suggestive of hepatitis B infection, e.g., dark urine, jaundice, right upper abdomen pain.
- Additional patients at the discretion of the investigator

Testing for hepatitis C should be performed using quantitative RNA-PCR at screening for all patients in the following risk categories:

- known or suspected past hepatitis C infection (including patients with past interferon 'curative' treatment),
- blood transfusions prior to 1990,
- current or prior IV drug users,
- current or prior dialysis,
- household contact of hepatitis C infected patient(s),
- current or prior high-risk sexual activity,
- body piercing or tattoos,

- At the discretion of the investigator, additional patients may also be tested for hepatitis C.

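### A patient who is HBc Ab positive with negative HBsAg and HBV-DNA can enrol, and nothing afterwards triggers an HBV-DNA test, even if ALT/AST rises on study drug

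*Combined protocol and SAP*

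**What the plan says.** **Who is tested.** Section 3.4.1 lists the risk categories, among them "known or suspected past hepatitis B infection". Section 4.6.1.2 says that at-risk patients "should be tested for hepatitis B serologic markers and viral load: HBV-DNA HBsAg, HBc Ab, and HBs Ab" before randomization.

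**What the result does.** The exclusion criteria in section 3.2.2 name "Chronic or active hepatitis B or C". They add that "HBV DNA and HCV RNA PCR testing are required at screening for all patients with a positive medical history" arising from risk factors or a confirmed earlier infection. Neither section says what follows from an HBc Ab positive result when HBsAg and HBV-DNA are negative.

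**The risk as the protocol describes it.** Section 3.2.5 states that "Sporadic cases of Hepatitis B reactivation have also been seen in this setting with everolimus" and that "Use of antivirals during anti-cancer therapy has been shown to reduce the risk of Hepatitis B virus reactivation and associated morbidity and mortality". It tells investigators to "be vigilant for symptoms and signs of infection", to treat an infection once diagnosed, and then to consider interrupting or stopping everolimus.

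**Monitoring.** The hepatitis row of Table 3-4 is marked at screening only. It names HBs Ab twice and leaves out HBc Ab. ALT and AST are in the laboratory panel at weeks 4, 16, 32 and 52 of treatment and at the later visits.

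**Dose rules.** Under Table 3-1 a non-hematological grade 2 event that the patient tolerates continues at the same dose. A grade 3 event is held until grade 1 or less and restarted one level lower. Grade 4, or an interruption of 3 weeks or more, ends treatment.

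**The concern.** HBc Ab is ordered, but no stated decision depends on it. The patients for whom it is most informative are those with past infection and no current evidence of virus, and the plan does not say how to handle them.

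A liver enzyme rise in such a patient has at least two explanations: drug toxicity or viral reactivation. Table 3-1 treats every rise as suspected everolimus toxicity and manages it by grade. Followed as written, it can keep a patient on an immunosuppressive drug, or restart that drug, without the test that would tell the two apart.

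Participants have no evidence of disease at entry and take study drug for up to 1 year, so the tolerance for an avoidable infective complication is low. This is a matter of patient safety and does not bear on the efficacy inference.

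**Working it through.** No figure in the plan is at issue. The check sets the provisions side by side and follows one patient through them.

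1. **Entry.** Take a patient with past hepatitis B infection who is HBc Ab positive, HBsAg negative and HBV-DNA negative. Section 3.4.1 puts this patient in a tested category. The exclusion in section 3.2.2 covers chronic or active infection but defines neither term by marker. Its note asks for PCR when earlier infection is confirmed, which implies that earlier infection alone does not exclude. So the patient can enrol, although two sites might classify the same patient differently.

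2. **At enrolment.** Sections 3.4.1 and 4.6.1.2 attach no flag and no monitoring to this pattern. Section 3.2.5 mentions antivirals as background and does not say who should be considered for them.

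3. **Scheduled tests on treatment (Table 3-4).**
   - ALT/AST after baseline: weeks 4, 16, 32 and 52, which is 4 panels.
   - HBV-DNA after screening: 0.

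4. **Tolerable grade 2 ALT/AST rise.** Table 3-1 keeps the same dose. The weekly follow-up in section 3.2.4 applies only after an interruption or discontinuation, so it does not start. Under section 3.4.4.1 a laboratory abnormality is an adverse event only if it causes signs or symptoms, is judged clinically significant or needs therapy. A silent rise may therefore not enter the follow-up duty either. No HBV-DNA is required.

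5. **Grade 3 ALT/AST rise.** Study drug is held, weekly follow-up begins if everolimus is suspected, and the drug restarts one level lower after recovery. No HBV-DNA is required before restart.

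6. **If reactivation is diagnosed.** Section 3.2.5 then applies: treat, and consider holding or stopping. This step exists, but nothing in steps 3 to 5 leads to it.

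7. **Comparison within the protocol.** Table 3-5 sets required investigations for pneumonitis grade by grade. Section 3.2.5 has a stop-and-treat instruction for invasive fungal infection. Hepatitis B reactivation, described in the same section, has no specific work-up.

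With the change described under the fix, scheduled HBV-DNA tests after screening go from 0 to 4 per flagged patient. All fall on draws that already take place, so extra scheduled draws are 4 − 4 = 0.

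**The case against.** The strongest reply is that the plan already protects these patients. Chronic or active hepatitis B, cirrhosis and active or uncontrolled severe infection are excluded, and ALT/AST must be at most 2.5 × ULN at entry. Eligibility questions go to the principal investigator. Investigators must watch for infection, judge causality of each adverse event and follow it to resolution. A competent investigator who knows of an HBc Ab result would order HBV-DNA as ordinary work-up. The Investigator's Brochure, to which section 3.2.5 refers, may say more. All of this is fair, and it narrows the gap to the diagnostic trigger. It does not close it, because none of these provisions requires the test, and Table 3-1 read literally allows dosing to go on without it.

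A second reply is that section 3.2.5 calls the cases sporadic and does not say in whom they occurred. They may have been in chronic carriers, who are excluded here. That stands, and it is why no count of harm is offered.

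A third is that scheduled tests on the existing draws would be 12, 16 and 20 weeks apart (16−4, 32−16, 52−32), and that the last falls at the planned end of treatment. At most three of the four can then change dosing. That also stands. The test triggered by an ALT/AST rise matters more than the scheduled ones.

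**Conclusion.** The gap is real but narrow. A patient with HBc Ab and negative HBsAg and HBV-DNA can enter, receive study drug for up to a year and have an ALT/AST rise managed by grade alone. Its size is 0 required HBV-DNA tests after screening, in a subset whose number the documents do not give. The conclusion assumes that the Investigator's Brochure, which is not shown, does not supply the rule.

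Three stronger readings are tempting, and the documents do not support them.

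- A reader might infer that the plan has no response to reactivation. It has one: section 3.2.5 directs treatment of a diagnosed infection. What is missing is the step that leads to the diagnosis.
- A reader might infer that hepatitis B reactivation on everolimus has caused liver failure and death. Section 3.2.5 says "Some of these infections have been severe (e.g. leading to respiratory or hepatic failure) and occasionally have had a fatal outcome", but that sentence covers bacterial, fungal and viral infections together and assigns no outcome to hepatitis B.
- A reader might infer that prophylaxis should be mandatory. Section 3.2.5 reports that antivirals help during anti-cancer therapy in general. It does not show that patients with this marker pattern need them, so that decision is best left to the investigator.

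This is a cheap improvement for patient safety, with no effect on power or the primary endpoint.

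**What to change.** 1. **Section 4.6.1.2.** State that a patient positive for HBsAg or HBV-DNA is ineligible, and that a patient who is HBc Ab positive with both negative is eligible but flagged.
2. **Table 3-4.** Add HBV-DNA for flagged patients to the existing blood draws at weeks 4, 16, 32 and 52. Correct the hepatitis row so that it names HBc Ab in place of the second HBs Ab.
3. **Table 3-1.** For flagged patients, send HBV-DNA at any ALT/AST rise of grade 2 or more. A tolerable grade 2 rise continues under the existing rule while the result is pending, so no new interruption is created. After a grade 3 rise, the result must be available before restart. If HBV-DNA is positive, hold study drug and treat, in line with section 3.2.5.

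The other rules (recovery to grade 1 or less, the 3-week limit, grade 4 discontinuation, weekly follow-up) stay as they are. Prophylaxis is left to the investigator.

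**Cost.** For n flagged patients, up to 4 × n scheduled assays plus one per qualifying rise. The documents do not give n. There are no extra scheduled visits. After a grade 3 rise the assay is sent while the drug is already held, but a slow result would count against the 3-week limit, and the documents give no turnaround time. The same rule applies in both arms, so blinding is unaffected.
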